Our **primary objective** is to determine the preliminary efficacy of the intervention. **Methods:** We will conduct a **two-group cluster randomized controlled trial** (RCT). From the available 13 large Head Start centers, six centers will be randomly selected and then randomly assigned to the intervention (n=3) or control group (n=3, usual Head Start activities); 24 caregiver-preschooler dyads will be recruited from each center (N=144 dyads).

AIM 1: Determine the preliminary efficacy of *FirstStep2Health* vs control among preschoolers on proximal behavioral changes of ↑ moderate-to-vigorous PA (MVPA) measured by accelerometry (primary outcome), ↑ diet quality (e.g., ↑ fruits/vegetables, ↑ fiber, ↑ whole grains, ↑ total protein, ↑ dairy, ↓ sugar-sweetened beverages, ↓ total sugars/fats), and ↓ screen time (e.g., watching TV, playing video games); and distal anthropometric outcomes of ↓ proportion of OW/O and ↓ body mass index (BMI) z-score. We anticipate an overall decrease in BMI z-score in intervention preschoolers because we expect OW/O preschoolers’ BMI z-score to decrease and healthy-weight preschoolers to have no change. We focus on proximal behavioral changes as our primary outcome instead of distal anthropometric outcomes due to the brevity of this study and the need for behavioral changes to be maintained for at least a year before manifesting in changes in anthropometric outcomes.^{49,50} **AIM 2: Examine the preliminary efficacy of *FirstStep2Health* vs control among caregivers** on their ↑ MVPA measured by accelerometry, ↑ diet quality (e.g., ↑fruits/vegetables, ↑fiber), ↓ screen time, ↓ proportion of OW/O, ↓ BMI, ↑ knowledge, ↑ feeding practice skill, ↑ self-efficacy, ↑ parental support of their child, ↑ parenting practices, and ↑ home environment. **AIM 3: Compare *FirstStep2Health* vs control on the bidirectional relationship** (as demonstrated in the APIM) between preschoolers and caregivers on MVPA, diet quality, and screen time. Further, we will **validate established feasibility, acceptability, and satisfaction of the intervention using qualitative and quantitative data**.

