C. APPROACH To ensure **rigor**, the study will use a rigorous design, reliable and valid instruments, and training and supervision to maintain ethical conduct and intervention integrity.

C.1. RESEARCH TEAM. Our multidisciplinary team includes researchers from nursing, nutrition, child development, engineering, and biostatistics. The team includes experts in preschooler obesity prevention (PI [name], Co-I [name], & Consultant [name]),^{4,38,106} Internet/social network-based intervention (PI [name] & Co-I [name]),^{38,107,108} mHealth (Co-I [name]),¹⁰⁹⁻¹¹¹ and cluster RCTs (Co-Is [name] & [name]).^{112,113}

C.2. PRELIMINARY STUDIES. In preparation for this application, we completed two systematic reviews^{16,33} and two preliminary studies.^{4,38,67,87} The systematic reviews^{16,33} suggest that OW/O interventions should target preschoolers via participatory learning³⁴ and provide caregivers with parenting skill training and behavioral change strategies. One preliminary study,⁴ with 32 Head Start caregivers, identified the unique needs and barriers to healthy behaviors in Head Start families and supported the intervention strategy of involving caregivers through an online support group supplemented with face-to-face meetings. The PI collaborated with the established research team on a quasi-experimental study to examine the feasibility and preliminary efficacy of the 10-week *FirstStep2Health* intervention.^{38,67,87} Sixty-nine dyads participated (39 in intervention). About 81% of caregivers and 46% of preschoolers were OW/O, and 92% reported no difficulty to get the foods they needed.³ **Feasibility.** Enrollment rate was 37% and retention rate was 99%. Preschooler participation was 77%, and caregiver participation was 87%. Completion rates for weekly tasks and quizzes were 82% and 88%, respectively. About 94% of caregivers were satisfied with the program; 97% would recommend the program to others. **Efficacy.** Intervention increased MVPA (raw $d=0.42$) and fruit/vegetable intake ($d=0.40$), and decreased screen time ($d=-0.21$) and BMI z-score ($d=-0.30$) in intervention preschoolers. It also increased caregivers' fruit/vegetable intake ($d=0.40$), but had a small effect on their MVPA ($d=0.08$) and BMI ($d=-0.07$).

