C.5. SETTING & SAMPLE. Six Head Start centers (≥ 4 classes/center) will be randomly selected from the Capital Area Community Services (CACs) Head Start and Early Childhood Programs and the Head Start for Kent County, which had 13 centers with ≥ 4 classes in 2017.^{126,127} Among the 13 centers, two had 4, one had 5, five had 6, one had 8, one had 9, two had 12, and one had 14 classes. The 13 centers cared for 1,932 preschoolers: 49% female, 20% Hispanic, 38% Black, and 39% White. Four classes will be randomly selected from each center, and 6 caregiver-preschooler dyads will be randomly selected from the eligible participants in each class (total: 6 centers, 24 classes, and 144 dyads). Inclusion and exclusion criteria are specified in **Table 1**.

C.6. SAMPLE SIZE & POWER. Due to the exploratory/developmental focus of this R21 grant proposal, our aim is to estimate effect sizes for proximal and distal outcomes in preschoolers to serve as foundation for future research. Assuming class cluster effects intraclass correlation (ICC)=0.01,^{128,129} and

significance level=.05, a sample size of 130 will provide a power of .80 to identify an effect size of 0.50, < 0.66 for MVPA achieved in the prior study after adjusting for demographics.³⁸ Given the extended intervention duration from 10 to 16 weeks and the strengthened intervention, we anticipate to also achieve an effect size of 0.50 in preschoolers' diet quality, screen time, and BMI z-score. We conservatively assume a 10% dropout.

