Head Start center environment, including the physical environment, provisions, practices, policies, training, and education. All other surveys will be completed by caregivers online via REDCap web application. Caregivers will be informed of online surveys via text-message or email. Data collectors and interviewers (blinded to group assignment) will be available by phone or in-person to answer questions.

Table 5. Study Measures

Concept	Measure and Description	# Items	Time	Reliability/Validity
Preschoolers (Aim 1)				
MVPA (min/day)	7-day ActiGraph GT3X-plus accelerometer ¹⁴⁵ Cut-points: sedentary activity (<37 counts/15 s), light (38–419), moderate (420–841), & vigorous (≥842) ^{146,147}	7-day	5 min	Reliability = 0.69–0.84 ¹⁴⁸ $r = 0.66$ with observational system ¹⁴⁵
Diet quality (e.g., fruit/vegetable, fiber, sugar/fat)	Intake at Head Start center: dietary observation system on snacks and lunch on two weekdays ¹⁴⁹ Intake at home: proxy-reported 24-hour dietary recall	3-day	90 min	ICC = 0.99; ¹⁴⁹ accurate rate: 95%; ¹⁵⁰ good agreement with actual energy intake ¹⁵¹
Screen Time	NHANES-Physical Activity and Physical Fitness survey ¹⁵²	2	1 min	Reliability: $r = 0.63–0.84$ ¹⁵³
Proportion of OW/O, BMI z-score	Calculated from height and weight using CDC growth charts ¹⁵⁴ Height: Child/Adult Shorr Measuring Board Stadiometer Weight: Child/Adult Seca model 874 portable electronic scale In accordance with NHANES measurement protocol ¹⁵⁵	N/A	3 min	Specificity 0.93; sensitivity 0.73 ¹⁵⁶
Caregivers (Aim 2)				
MVPA	7-day ActiGraph GT3X-plus accelerometer Cut-points: light (0–2689 counts/60 s), moderate (2690–6166), & vigorous (≥6167) ¹⁵⁷	7-day	5 min	ICC = 0.97–0.99 ¹⁵⁸ $r = 0.81$ with oxygen consumption ¹⁵⁹
Diet quality	Fruit-vegetable-fiber screener ¹⁶⁰	10	3 min	$r = 0.71$ with full Block survey ¹⁶⁰
Screen Time	NHANES-Physical Activity and Physical Fitness survey ¹⁵²	2	1 min	Reliability: $r = 0.63–0.84$ ¹⁵³
Proportion of OW/O, BMI	Calculated using (weight kg/height m^2) ¹⁶¹ Measures are similar to those used in preschoolers	N/A	3 min	Specificity 0.97; sensitivity 0.42 ¹⁶²
Knowledge	Knowledge on preschoolers' dietary intake & physical activity ¹⁶³	25	5 min	N/A
Feeding Practice Skill	Child Feeding Questionnaire ¹⁶⁴ measuring caregiver feeding practice behaviors	33	5 min	$\alpha = 0.71–0.93$ ^{38,164,165} $r = -0.26–0.53$ with child BMI ^{164–166}
Self-Efficacy	Parental self-efficacy scale ¹⁶³	20	4 min	$\alpha = 0.72–0.94$ ^{38,163}

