Parental Support	Parental support scale for eating habits and physical activity ¹⁶⁷	12	3 min	$\alpha = 0.83–0.87$ ^{38,167,168}
Parenting Practices	Parenting Style and Dimensions Questionnaire ¹⁶⁹ assessing parenting styles: authoritative, authoritarian, and permissive	32	5 min	$\alpha = 0.64–0.91$ ¹⁷⁰
Home Environment	Family Nutrition and Physical Activity (FNPA) screening tool ¹⁷¹ assessing home obesogenic environments and practices	20	4 min	Correlated with child BMI ^{171,172}
Demographics	Socio-demographic questionnaire (e.g., age, sex, race)	12	3 min	N/A
Center Environment	EPAO-SR ¹⁴⁴	1-day	30 min	Related to observational data ¹⁴⁴

C.15. DATA ANALYSIS. Any missing at random (MAR) data will be imputed using procedures suggested by Potthoff.¹⁷³ For non-MAR data, a sensitivity analysis will be performed following recommended approaches for continuous and discrete outcomes.^{174–177} All analyses will use the intention-to-treat¹⁷⁸ principle. Data analysis will be disaggregated by sex in preschoolers. **AIM 1 & 2:** Mixed-effect models in SAS 9.4 will be used to evaluate the intervention efficacy. Fixed effect predictors will include group, time, groupXtime interaction, and potential confounders such as preschooler sex, race, baseline weight status, and caregiver marital status. The correlation of preschooler outcomes measured over time and dependence due to nesting in the same center or class will be accounted through center- and class-specific random cluster effect. Contrasts will quantify the intervention effects separately at the post-intervention. Holm's method will be used to statistically control for multiple comparisons.¹⁷⁹ Effect size (Cohen's d) will be calculated. **AIM 3:** Path analysis will be conducted using EQS 6.2. Model fit will be assessed using root mean square error approximation, Normed Fit Index, and Tucker Lewis index. Chi-square difference test¹⁸⁰ will be used to compare models. Model modification will be made if needed. Feasibility/acceptability/satisfaction will be determined through enrollment, intervention participation, and evaluation survey data. Recorded individual interviews will be analyzed using directed content analysis in ATLAS.ti 8 to evaluate reasons for satisfaction and suggestions for improvement.

Table 6. Method Considerations

Issue	Justification and Strategies

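### Does the open-ended definition of preschooler diet quality leave the Aim 1 Holm correction and the diet effect size undefined?

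*Combined protocol and SAP*

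**What the plan says.** C.15 (Data Analysis, Aims 1 and 2) plans mixed-effect models. It states "Contrasts will quantify the intervention effects separately at the post-intervention", then that Holm's "method will be used to statistically control for multiple comparisons", and then that Cohen's d will be calculated. It does not name the outcomes that Holm covers.

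Preschooler diet quality is described in two places:

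- Specific Aims, Aim 1: "diet quality (e.g., ↑ fruits/vegetables, ↑ fiber, ↑ whole grains, ↑ total protein, ↑ dairy, ↓ sugar-sweetened beverages, ↓ total sugars/fats".
- Table 5, preschooler section: "Diet quality (e.g., fruit/vegetable, fiber, sugar/fat".

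Both are lists of examples, and neither names an index or composite. C.14 refers to Table 5 and Appendix A for the measures; Appendix A is not part of the public document.

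C.6 gives the purpose of the trial: "our aim is to estimate effect sizes for proximal and distal outcomes in preschoolers to serve as foundation for future research". Its calculation reads "significance level=.05, a sample size of 130 will provide a power of .80" at an effect size of 0.50 for MVPA, which Aim 1 tags as the primary outcome. C.6 then adds "we anticipate to also achieve an effect size of 0.50 in" diet quality, screen time and BMI z-score. The prior-study results in C.2 give one child diet effect: "fruit/vegetable intake ($d=0.40$), and decreased screen time ($d=-0.21$) and BMI z-score ($d=-0.30$) in intervention preschoolers".

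**The concern.** C.6 treats diet quality as one variable with one expected effect, while Aim 1 and Table 5 make it several. Two consequences seem to follow.

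First, the size of the Holm family depends on how diet is counted, and so does the hurdle for screen time, overweight/obesity and BMI z-score. If Holm instead applies only within each outcome's model, the diet components are tested against one another without correction.

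Second, the main product of the trial is a set of effect sizes for planning later work. If one diet component were picked after the results were seen, its effect size would be biased upward, and Holm, which adjusts p-values, would not correct that. A later trial sized on the inflated figure would be too small.

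**Working it through.** **The plan's own figure.** Inputs from C.5 and C.6: effect size 0.50, significance level .05, class ICC 0.01, 24 classes, 130 children analysed. An unclustered two-sided comparison needs 63 per arm, 126 in all. With 6 per class the design effect is 1 + (6 − 1) × 0.01 = 1.05, so N = 126 × 1.05 = 132.3. With 130/24 = 5.42 per class it is 1.044, so N = 131.6. Power at N = 130 is .794 to .797. C.6 therefore reproduces as one unadjusted two-sided test; a one-sided test would give .874. Dropout also agrees: 144 × 0.9 = 129.6.

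**Family sizes.** Outside diet and MVPA, Aim 1 has three outcomes: screen time, proportion overweight/obese and BMI z-score. Aim 2 names eleven caregiver outcomes.

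| Diet counted as | MVPA outside Holm | MVPA inside Holm | Aim 1 without MVPA, pooled with Aim 2 |
|---|---|---|---|
| one score | 3 + 1 = 4 | 5 | 4 + 11 = 15 |
| three (Table 5) | 3 + 3 = 6 | 7 | 6 + 11 = 17 |
| seven (Aim 1) | 3 + 7 = 10 | 11 | 10 + 11 = 21 |

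Since the lists are examples, these are not upper limits.

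**Power under Holm.** Effective n per arm is 65/1.044 = 62.25, and the standard error of d is √(2/62.25) = 0.179. With a t-test on 128 df, uncorrected power at 0.50 is .79. Simulated Holm power for screen time or BMI z-score, at correlation 0 or 0.3, is in the table. The higher value has every outcome at 0.50. The lower has only one diet component with an effect. The 0.50 for overweight/obesity is an assumption.

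| Tests | First Holm threshold | Power |
|---|---|---|
| 4 | .05/4 = .0125 | .70 to .71 |
| 6 | .05/6 = .0083 | .60 to .66 |
| 10 | .05/10 = .005 | .50 to .59 |

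If the aims are pooled (15, 17 or 21 tests, correlation 0.3), power is about .53, .50 and .47 with every outcome at 0.50. It is about .43, .41 and .39 with the caregiver outcomes and the extra diet items null. Going from one diet test to seven then costs about 4 to 6 points.

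For MVPA, the .80 holds only outside Holm. Inside a family of 5, 7 or 11, power at the first Holm step is .58, .54 or .48; later steps are less strict.

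**Picking the largest diet effect.** If seven components share one true effect, the largest estimate is expected to exceed it by 0.242 × √(1 − correlation): 0.24 at correlation 0, 0.20 at 0.3, 0.15 at 0.6. If the true effect were 0.40 throughout, selection at correlation 0.3 would report about 0.60. A later individually randomised trial with power .80 at 0.60 has 45 per arm, and power .47 at 0.40, where 100 per arm are needed.

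**No correction among diet components.** The chance of at least one p < .05 among seven with no effect is 1 − 0.95^7 = .30 if independent, .27 at correlation 0.3 and .21 at 0.6.

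**Reporting every component.** The shift disappears when no component is selected. Each d then has a 95% half-width of about 1.96 × 0.179 = 0.35, which is wider than the 0.20 shift.

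**The case for a change.** The strongest case for a change is that effect sizes are what this trial is meant to deliver, so calling it exploratory does not excuse an unfixed outcome. The other preschooler rows of Table 5 are specific: MVPA has cut-points and BMI z-score a growth reference. The two diet lists differ, nothing in the text prevents a late choice of component, and a definition would cost only a few sentences.

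The textual part of this stands. The supplied text does not name the diet variable, and C.15 does not list the family.

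The argument about consequences is weaker:

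- The counts of 4, 6 and 10 require MVPA to be outside Holm, which C.15 does not state. Whether Aims 1 and 2 are pooled can matter more than how diet is counted.
- Holm would not be empty within an outcome, because C.15 also calls for analysis by sex.
- No passage says that a single diet component will be carried forward. The sentence on Cohen's d reads naturally as applying to every outcome analysed.
- The powers take over C.6's basis (class ICC only, no use of baseline). The planned model has baseline data, which could raise them, and center effects with six randomised centers, which would lower them. They are illustrations.
- A scoring rule in Appendix A cannot be ruled out.

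**Conclusion.** This is missing detail that an analyst can fill sensibly within the plan as written. Holm keeps its error control at every family size above; a longer list costs power on secondary outcomes but does not invalidate any result. Analysing each diet variable, reporting its d and applying Holm across the set follows C.15 and removes the selection problem. Naming a single score, or fruit/vegetable intake, would be one reasonable choice among several, and the documents give no reason to call the others wrong.

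The size of the ambiguity is six tests in the Aim 1 family, worth about 11 to 20 percentage points of power for a secondary outcome at 0.50 if Aim 1 stands alone and MVPA is outside Holm, and about 4 to 6 points if the aims are pooled. The possible bias of about 0.20 in a diet effect size depends on a deliberate choice of the largest of seven and on an assumed correlation of 0.3. The C.6 calculation is consistent with MVPA as a single primary test at .05, and on that reading the primary comparison is untouched.
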